4.1.7 Storage conditions

Afatinib will be kept in their original packaging and a secure, limited access storage area according to the recommended storage conditions on the medication label.

Cetuximab vials will be stored under refrigeration at 2° C to 8° C (36° F to 46° F). **Do not freeze.** Increased particulate formation may occur at temperatures at or below 0° C. This product contains no preservatives. Preparations of cetuximab in infusion containers are chemically and physically stable for up to 12 hours at 2° C to 8° C (36° F to 46° F) and up to 8 hours at controlled room temperature (20° C to 25° C; 68° F to 77° F). Discard any remaining solution in the infusion container after 8 hours at controlled room temperature or after 12 hours at 2° C to 8° C. Discard any unused portion of the vial.

4.1.8 Drug accountability

All study drug (Afatinib) will be provided by Boehringer Ingelheim (manufacturer). Cetuximab is commercially available.

The recipient will acknowledge receipt of the drug (afatinib) by returning the drug receipt form indicating shipment content and condition. Damaged supplies will be replaced. Study drug accountability records should be maintained by the site in accordance with the local SOPs and regulations.

At the time of study closure, any unused or expired study drug will be destroyed at the site per Institutional SOPs. Any partially used study drug will be destroyed at the site, either during the course of the study or at the time of study closure, per Institutional SOPs.

4.2 CONCOMITANT THERAPY, RESTRICTIONS, AND RESCUE TREATMENT**4.2.1 Rescue medication, emergency procedures, and additional treatment(s)**Rescue medication

Rescue medications to reverse the actions of afatinib are not available. There is no specific antidote for overdosage with afatinib. In cases of suspected overdose, afatinib should be withheld and supportive care initiated. If indicated, elimination of unabsorbed afatinib may be achieved by emesis or gastric lavage. Potential adverse events should be treated symptomatically.

Common adverse events of treatment with afatinib with specified management recommendations and/or requirements include diarrhea, stomatitis/mucositis, and rash/acne. To improve tolerability and the probability of clinical benefit, patients should receive prompt and appropriate supportive care at the first signs of symptoms. Suggested treatments for AEs are described below.

Concomitant treatments

Concomitant medications or therapy to provide adequate supportive care may be given as clinically necessary.

After study enrollment, palliative radiotherapy may be given for bone pain or for other reasons (e.g. bronchial obstruction, skin lesions), provided that the total dose delivered is in a palliative range according to institutional standards. The irradiated area cannot be used for tumor response assessment. During palliative radiotherapy, study treatment should be delayed and may be resumed once the patient has recovered from any radiation associated toxicity. If medication is interrupted for more than 14 days, the decision to continue will be made by the sponsor in

agreement with the investigator. Continuous interruption of >28 days due to palliative radiotherapy will not be allowed.

All concomitant therapy, including anaesthetic agents, vitamins, homeopathic/herbal remedies, nutritional supplements, must be recorded in the (e)CRF during the screening and treatment period, starting from the date of signature of informed consent, and ending at the EOT visit. After the EOT visit, only concomitant therapy indicated for treatment of an AE has to be reported.

In case of major surgery (as judged by the investigator), it is recommended to stop treatment with afatinib around one week prior to the surgery, and to restart treatment after complete wound healing. If afatinib is interrupted for more than 14 days, the decision to continue will be made by the sponsor in agreement with the investigator.

4.2.2 Restrictions

4.2.2.1 Restrictions regarding concomitant treatment

Concomitant medications, or therapy to provide adequate supportive care, may be given as clinically necessary.

Palliative radiotherapy may be given as described in Section 4.2.1.

Additional experimental anti-cancer treatment and/or standard chemo-, immunotherapy, hormone treatment (with the exception of megestrol acetate and use of anti-androgens and/or gonadorelin analogues for treatment of prostate cancer), or radiotherapy (other than palliative radiotherapy for symptom control) is not allowed concomitantly with the administration of study treatment.

Afatinib is a substrate of the P-gp transporter. Caution should be exercised when combining afatinib with P-gp modulators. For a list of potent P-gp inhibitors and inducers see Appendix 10.1.

4.2.2.2 Restrictions on diet and life style

Patients should be advised to avoid any foods known to aggravate diarrhea.

To prevent skin related adverse events, it is recommended to avoid intense irradiation with UV light and harsh detergents, see also Section 4.2.3.2.

4.2.2.3 Restrictions regarding women of child-bearing potential

Patients who are not of childbearing potential due to being postmenopausal (i.e. 12 months with no menses without alternative medical cause, predefined hormonal level according to local regulation or etc.) or being permanently sterilized (bilateral oophorectomy, bilateral

salpingectomy, hysterectomy and/or tubal ligation) do not need to use contraception to be eligible for the trial.

All other patients are considered to have childbearing potential and must use adequate contraception throughout the trial (from screening until end of trial participation or 4 weeks after last dose of trial medication, whichever is later).

Highly effective methods of birth control should be applied to women of childbearing potential as those, alone or in combination, that result in a low failure rate (i.e., less than 1% per year – placement of intrauterine device or intrauterine system, “double barrier” methods of contraception, male sterilisation or etc.) when used consistently and correctly, and must be in accordance with local regulations where applicable. The list of contraception methods meeting these criteria is provided in the patient information.

Women who become pregnant while participating in the study must discontinue study medication immediately. The pregnancy must be reported following procedures detailed in section 5.3.7.4

4.2.3 Management of expected adverse events

Dermatologic adverse events and diarrhea are the most common side-effects associated with treatment with afatinib. Treatment of these side-effects should be proactive and should be started as early as possible after onset of symptoms.

4.2.3.1 Management of diarrhea and hydration status following treatment with afatinib

Diarrhea occurs at a high frequency and generally begins within 2 weeks of exposure to afatinib. Although usually mild to moderate, diarrhea may lead to dehydration and compel treatment modification or discontinuation, so early management is essential (Table 4.2.3.1: 1). At the time of initiation of treatment with afatinib patients should be given a supply of loperamide to keep with them at all times or access to afatinib should be confirmed; and patients should be counselled on the appropriate use.

Patients must be advised to drink an adequate amount of fluids to make up for the fluid lost through diarrhea.

Table 4.2.3.1: 1 Grade specific treatment recommendations for afatinib related diarrhea

Severity (CTCAE Grading)	Description	Intervention concerning afatinib treatment	Specific intervention

Mild (Grade 1)	Increase of < 4 stools per day over baseline; mild increase in ostomy output compared with baseline	Continue same dose	Stop laxatives and advise patient to drink at least 8-10 glasses of water or clear fluids per day; 4 mg (2 tablets) of loperamide to be taken immediately, followed by 2 mg (1 tablet) after each loose stool until bowel movements cease for 12 hours
Moderate (Grade 2)	Increase of 4-6 stools per day over baseline; i.v. fluids indicated < 24 hours; moderate increase in ostomy output compared with baseline; not interfering with ADL	Continue same dose unless Grade 2 diarrhea continues for ≥ 2 days (48 hours) in which case treatment must be interrupted until recovered to ≤ Grade 1 followed by dose reduction	Continue loperamide; assess for dehydration and electrolyte imbalance; consider IV fluids and electrolyte replacement
Severe (Grade 3)	Increase of ≥ 7 stools per day over baseline; incontinence; IV fluids > 24 hours; hospitalization; severe increase in ostomy output compared with baseline; interfering with ADL	Dose interruption until recovered to ≤ Grade 1 followed by dose reduction*	See Grade 2; plus: an infectious process should be ruled out with stool cultures; aggressive iv fluid replacement ≥ 24 hours; hospitalization to monitor progress; consider prophylactic antibiotics if patient is also neutropenic;
Life threatening (Grade 4)	Life-threatening consequences (e.g. haemodynamic collapse)	Dose interruption until recovered to ≤ Grade 1 followed by dose reduction*	See Grade 3

* If despite optimal supportive care and a treatment interruption, diarrhea does not resolve to CTC AE Grade ≤ 1 within 14 days, treatment with afatinib must be permanently discontinued. In the event that the patient is deriving obvious clinical benefit according to the investigator's judgment, further treatment with afatinib will be decided in agreement between the sponsor and the investigator.

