4.1.4.1.2 Dose reduction for afatinib

Treatment related AEs will be managed by treatment interruptions and subsequent dose reductions of afatinib according to the schedule described in Table 4.1.4.1.2: 1. Given overlapping toxicities, afatinib dose reductions should precede cetuximab dose reductions. Dose reductions will apply to individual patients only. Once the dose has been reduced, it cannot be increased later.

To prevent the development of more severe adverse events, treatment related diarrhea or rash should be managed early and proactively as described in Section 4.2.3.

Table 4.1.4.1.2: 1 Dose reduction scheme for afatinib

AE type and CTCAE Grade	Action	Dose reduction scheme
Events related to study drug: 
 Diarrhea Grade 2 persisting for 2 or more consecutive days (48 hours) despite adequate anti-diarrheal medication/hydration Reduced renal function to \geq Grade 2 as measured by serum creatinine, proteinuria or decrease in glomerular filtration rate of more than 50% from baseline Any other drug related AE Grade \geq3 	Pause treatment until patient has recovered to Grade \leq 2 (Grade \leq 1 for diarrhea or impaired renal function only) or baseline ¹ . Resume treatment at reduced dose according to schedule opposite. If patient has not recovered to Grade \leq 2 (Grade \leq 1 for diarrhea or impaired renal function) or baseline ¹ within 14 days, study treatment	If patient was receiving Afatinib 30 mg daily, resume treatment at a dose of 20 mg daily. If patient was receiving Afatinib 20 mg daily, resume treatment at 20 mg intermittent dosing, 5 days on, 2 days off. If patient was receiving Afatinib 20 mg intermittent dosing, discontinue treatment.

AE type and CTCAE Grade	Action	Dose reduction scheme
	must be permanently discontinued ² .	
Acute onset and/or unexplained worsening of pulmonary systems (dyspnoea, cough, fever)	Pause afatinib while clinical assessment to exclude ILD is completed.	If ILD is ruled out as a cause of symptoms, grade symptoms and relatedness and report as AEs. If AEs are not related, resume afatinib at current dose. If AEs are drug related, follow directions in row above. If ILD is confirmed, discontinue afatinib

¹ Baseline is defined as the CTCAE Grade at the start of treatment

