4.3 TREATMENT COMPLIANCE

Patients will be dispensed Afatinib on a monthly basis in pill bottles with 30 tablets each. At every follow-up visit, they will be asked to bring in their pill bottles and pill count will be

performed. Pill diary will also be provided to document every dose taken. Missed doses and compliance to treatment will be documented.

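### Section 4.2.3.1 appears to name the wrong drug: confirming access to afatinib satisfies the start-of-treatment instruction without securing the loperamide that Table 4.2.3.1: 1 relies on

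*Combined protocol and SAP*

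**What the plan says.** Section 4.2.3.1 sets out what happens at the start of afatinib: "patients should be given a supply of loperamide to keep with them at all times or access to afatinib should be confirmed". The sentence ends by asking that patients be counselled on appropriate use, without saying of which drug.

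Table 4.2.3.1: 1, in the same section, is titled "Grade specific treatment recommendations for afatinib related diarrhea". Its Grade 1 row reads "4 mg (2 tablets) of loperamide to be taken immediately, followed by 2 mg (1 tablet) after each loose stool". Its Grade 2 row reads "Continue loperamide; assess for dehydration and electrolyte imbalance". The Grade 3 row refers back to Grade 2, and the Grade 4 row refers back to Grade 3.

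Two other places bear on the point. Section 4.3 states that "Patients will be dispensed Afatinib on a monthly basis in pill bottles with 30 tablets each". Table 4.1.4.1.2: 1 lists, among the events that lead to a pause and a dose reduction, "Diarrhea Grade 2 persisting for 2 or more consecutive days (48 hours) despite adequate anti-diarrheal medication/hydration". The text above that table adds: "Once the dose has been reduced, it cannot be increased later".

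**The concern.** The sentence is the section's only instruction on having a medicine ready before diarrhea starts. It offers two alternatives, and the second names the drug held responsible for the diarrhea. Someone following the words exactly could confirm that the patient has afatinib, treat the instruction as met, and leave the patient without the medicine that the table calls for at onset.

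The protocol itself explains why readiness matters. Section 4.2.3.1 describes diarrhea as common with afatinib, typically appearing in the first two weeks, and it stresses early management because diarrhea can force a change or stop in treatment. Sections 4.1.4.1.2, 4.2.1 and 4.2.3 likewise ask for early or prompt management. What is at stake is therefore chiefly patient safety, at a time when symptoms are expected.

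**Working it through.** No arithmetic applies: the point involves no sample size, power, alpha or event figure, and the plan states no number to reproduce. The check is to set the places side by side.

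1. **Structure of the instruction.** Section 4.2.3.1 joins two actions with *or*: (a) supply loperamide, or (b) confirm access to afatinib. Doing either one satisfies it.

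2. **Whether (b) adds anything.** Section 4.3 has afatinib dispensed monthly to all patients, and Section 4.1.4.1 has it dispensed on day 1 of each cycle. A patient starting treatment therefore always has access to afatinib. Alternative (b) is met in every case, and meeting it provides no anti-diarrheal.

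3. **What the table presupposes.**

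| Place | Role of loperamide |
|---|---|
| Section 4.2.3.1, sentence on treatment start | One of two alternatives; not assured |
| Table 4.2.3.1: 1, Grade 1 | Taken immediately, then after each loose stool |
| Table 4.2.3.1: 1, Grade 2 | Continued, hence already started |
| Table 4.2.3.1: 1, Grades 3 and 4 | Carried forward by reference to the row above |
| Table 4.1.4.1.2: 1 | Adequate anti-diarrheal medication assumed before the Grade 2 trigger applies |

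The table relies on loperamide being at hand. The sentence, taken literally, does not make sure that it is.

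4. **Whether another place repairs it.** Sections 4.1.4.1.2, 4.2.1 and 4.2.3 ask for early or prompt management in general terms, but none assures a loperamide supply at treatment start. No other section corrects or explains the sentence. It stands in the current text of Version 7.0, and nothing suggests a redaction or a fault of text extraction.

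5. **Whether the two places exclude each other.** They do not. A site that chooses (a) complies with the sentence and with the table. A site that relies on (b) is not barred from also giving loperamide. The gap opens only where (b) is taken as sufficient.

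**The case against.** The strongest reply is that this is a one-word slip that any clinician would read past. The sentence sits in a section on managing diarrhea, opens with a loperamide supply and closes with counselling on use. The sensible reading is that the second drug name was meant to repeat the first. The table directly below names loperamide, and the surrounding text presses for early treatment. Most of this stands: it makes harm unlikely and supports a low severity. It does not make the sentence correct, and an operative safety instruction should not depend on the reader noticing that a drug name is wrong.

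A reader might infer four stronger things that the documents do not support.

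- *That the protocol deliberately allows afatinib access in place of loperamide.* Nothing indicates a chosen rule; the wording looks like an error.
- *That the sentence and the table cannot both be followed.* They can, by supplying loperamide.
- *That the table requires loperamide at the first loose stool.* It says immediately at Grade 1 and then after each loose stool, and it is a table of recommendations.
- *That the slip costs afatinib exposure before the first response scan at 8 weeks, through an irreversible dose reduction.* No figure supports this. Table 4.1.4.1.2: 1 makes the Grade 2 trigger conditional on adequate anti-diarrheal treatment, so a patient without loperamide would not clearly meet it. The Grade 2 row of Table 4.2.3.1: 1 omits that condition, so the chain is conceivable under that row, but it remains unquantified.

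The site and patient instructions are not among the documents reviewed, so it cannot be said that they carry the same error.

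**Conclusion.** The sentence is wrong as written. Literal compliance does not secure the anti-diarrheal on which Table 4.2.3.1: 1 relies, because its second alternative is met for every patient by the trial's own dispensing. This is an internal inconsistency of minor severity, most plausibly a drug-name slip.

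As to size, the wording applies to each of the planned 50 patients who starts treatment under this text. Any consequence requires someone to act on the literal reading, and how often that would happen cannot be derived. No effect on the ORR endpoint, its test or the sample size is shown. Any effect on diarrhea grades, interruptions or dose reductions is possible but cannot be estimated from the documents.

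The conclusion rests on reading *or* in its ordinary sense and on no other section supplying the missing assurance; none was found.

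**What to change.** Reconcile the sentence in Section 4.2.3.1 with Table 4.2.3.1: 1, so that the medicine whose supply or access is confirmed at treatment start is the one the table refers to. Make clear which medicine the counselling concerns. Check any site or patient instructions derived from this section for the same wording, and correct them if it appears there. This asks only that the two places agree and introduces no new clinical rule.

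The cost is one sentence in the protocol plus a check of derived materials. No analysis, endpoint or sample-size figure changes.

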4.2.3.2 Management recommendations for dermatological AEs following treatment with afatinib

Dermatologic AEs of afatinib include rash, acne, dermatitis acneiform, and dry skin. General recommendations for prophylaxis are summarized in Table 4.2.3.2: 1 and grade-specific treatment recommendations are summarized in Table 4.2.3.2: 2. For dose adjustment of afatinib refer to Table 4.1.4.1.2.

Specific interventions should be reassessed at least after 2 weeks or at any worsening of symptoms, in which case the specific intervention should be adjusted and, depending on own clinical experience, early involvement of a dermatologist should be considered. (4)

Table 4.2.3.2: 1 General recommendations for prophylaxis while receiving afatinib

Personal hygiene	
Use of gentle soaps and shampoos for the body, e.g. pH5 neutral bath and shower formulations and tepid water.
 
Use of very mild shampoos for hair wash.
 
Only clean and smooth towels are recommended because of potential risk of infection. The skin should be patted dry after a shower, whereas rubbing the skin dry should be avoided.
 
Fine cotton clothes should be worn instead of synthetic material.
 
Shaving has to be done very carefully.
 
Manicure, i.e. cutting of nails, should be done straight across until the nails no longer extend over the fingers or toes. Cuticles are not allowed to be trimmed because this procedure increases the risk of nail bed infections

Sun protection	
Sunscreen should be applied daily to exposed skin areas regardless of season. Hypoallergenic sunscreen with a high SPF (at least SPF30, PABA free, UVA/UVB protection), preferably broad spectrum containing zinc oxide or titanium dioxide are recommended
 
Patients should be encouraged to consequently stay out of the sun.
 
Protective clothing for sun protection and wearing a hat should be recommended.

Moisturizer treatment	
It is important to moisturize the skin as soon as anti-EGFR therapy is started.

	
Hypoallergenic moisturizing creams, ointments and emollients should be used once daily to smooth the skin and to prevent and alleviate skin dryness.
 
Note: avoid greasy creams (e.g. petrolatum, soft paraffin, mineral oil based) and topical acne medications

Prevention of paronychia	
Patients should keep their hands dry and out of water if ever possible.
 
They should avoid friction and pressure on the nail fold as well as picking or manipulating the nail.
 
Topical application of petrolatum is recommended around the nails due to its lubricant and smoothing effect on the skin.

Table 4.2.3.2: 2 Grade specific treatment recommendations of skin reactions to afatinib

Severity (CTCAE Grading)	Description	Specific intervention
ACNEIFORM RASH		
Mild (Grade 1)	Macular or papular eruptions or erythema without associated symptoms	Consider topical antibiotics, e.g. clindamycin 2% or topical erythromycin 1% cream or metronidazole 0.75% or topical nadifloxacin 1%; Isolated scattered lesion: cream preferred Multiple scattered areas: lotion preferred
Moderate (Grade 2)	Macular or papular eruptions with pruritus or other associated symptoms; localized desquamation or other lesions covering <50% of BSA	Topical treatment as for Grade 1 plus short term topical steroids, e.g. prednicarbate cream 0.02% plus an oral antibiotic (for at least 2 weeks) e.g. Doxycycline 100mg b.i.d. or Minocycline hydrochloride 100mg b.i.d
Severe (Grade 3)	Severe, generalized erythroderma or macular, papular or vesicular eruption; desquamation covering ≥ 50% of BSA; associated with pain, disfigurement, ulceration or desquamation	Topical and systemic treatment as for Grade 2. Consider referral to dermatologist Consider systemic steroids

Life threatening (Grade 4)	Generalized exfoliative, ulcerative, or bullous dermatitis	See Grade 3 Systemic steroids are recommended
EARLY AND LATE XEROTIC SKIN REACTIONS - PRURITUS		
Mild (Grade 1)	Mild or localized	Topical polidocanol cream. Consider oral antihistamines, e.g. diphenhydramine, dimethindene, cetirizine, levocetirizine, desloratadine, fexofenadine or clemastine)
Moderate (Grade 2)	Intense or widespread	See Grade 1 plus oral antihistamines; Consider topical steroids, e.g. topical hydrocortisone
Severe (Grade 3)	Intense or widespread and interfering with activities of daily living (ADL)	See Grade 2.
XEROSIS (DRY SKIN)		
Mild (Grade 1)	Asymptomatic	Soap-free shower gel and/or bath oil. Avoid alcoholic solutions and soaps. Urea- or glycerin-based moisturizer. In inflammatory lesions consider topical steroids (e.g. hydrocortisone cream)
Moderate (Grade 2)	Symptomatic, not interfering with ADL	See Grade 1. In inflammatory lesions consider topical steroids (e.g. hydrocortisone cream)
Severe (Grade 3)	Symptomatic, interfering with ADL	See Grade 2. Topical steroids of higher potency (e.g. prednicarbate, mometasone furoate) Consider oral antibiotics
FISSURES		
Mild (Grade 1)	Asymptomatic	Petroleum jelly, Vaseline® or Aquaphor for 30 minutes under plastic occlusion every night, followed by application of hydrocolloid dressing; antiseptic baths (e.g. potassium permanganate therapeutic baths, final concentration of 1:10,000, or povidone-iodine baths)

		Topical application of aqueous silver nitrate solutions to fissures
Moderate (Grade 2)	Symptomatic, not interfering with ADL	See Grade 1. Consider oral antibiotics.
Severe (Grade 3)	Symptomatic, Interfering with ADL	See Grade 2.
1 If Grade 2 rash persists for ≥ 7 days despite treatment and is poorly tolerated by the patient, the investigator may choose to pause treatment up to 14 days followed by a reduction in the dose of afatinib according to the dose reduction scheme in Table 4.1.4.1.2: 1		

